6.3.1.2.4. Subgroup Analyses

To assess consistency of rVE across subgroups, the primary efficacy endpoint will be analyzed in selected subgroups based on the PP Set, using similar methods as described for the primary analysis. The estimated rVE and 95% CI will be provided within each category of the planned subgroups (see [Table 2](#) for subgroups).

If the number of participants in a particular subgroup is less than 15% of the enrollment sample size, then the subgroup may be combined with other subgroups for analyses. The subgroup analyses will not provide inference for the interactions between subgroups.

Forest plots will be provided for rVE and its 95% CI for each subgroup based on the PP Set.

The above subgroup analyses will be repeated on the mITT Set if NI is demonstrated.

6.3.2. Analysis of the Key Secondary Efficacy Endpoints

A sequential/hierarchical statistical multiple testing procedure will be used to control the overall Type 1 error rate over the primary efficacy endpoint and key secondary efficacy endpoints.

Key secondary efficacy endpoints will only be tested for NI and superiority at the final analysis using one-sided 2.5% Type I error rate when the primary efficacy endpoint achieves statistical significance. See [Section 6.6](#) for the multiplicity adjustments among the primary efficacy endpoint and the key secondary efficacy endpoints.

6.3.2.1. Derivation of Cases for Key Secondary Efficacy Endpoints

The first key secondary efficacy endpoint is the rVE of mRNA-1010 vs. the active comparator in preventing the first occurrence of RT-PCR confirmed protocol-defined ILI starting 14 days post vaccination through Day 181 (Month 6) or at the end of the influenza season, whichever occurs later, caused by influenza A or B virus strains with similarity to the vaccine strains selected for the seasonal influenza vaccine.

The second key secondary efficacy endpoint is the rVE of mRNA-1010 vs. the active comparator in preventing the first occurrence of RT-PCR confirmed protocol-defined ILI starting 14 days post vaccination through Day 181 (Month 6) or at the end of the influenza season, whichever occurs later, caused by influenza A or B virus strains antigenically matched to the vaccine strains selected for the seasonal influenza vaccine.

Following a positive RT-PCR result obtained by the central laboratory, the antigenicity test on cultured laboratory isolates and sequencing of HA region will be performed on the NP-swab sample stored at the central laboratory.

The derivation rules for the first RT-PCR confirmed protocol-defined ILI caused by influenza A or B virus strains with similarity to selected vaccine strains are as follows:

- Must be the first RT-PCR confirmed protocol-defined ILI ([Section 6.3.1.1](#))
- Similarity is confirmed by culture antigenic test and/or genetic sequencing, following the rules specified in [Table 3](#) below.

The derivation rules for the first RT-PCR confirmed protocol-defined ILI caused by influenza A or B virus strains antigenically matched to selected vaccine strains are as follows:

- Must be the first RT-PCR confirmed protocol-defined ILI ([Section 6.3.1.1](#))
- Antigenic match is confirmed by culture antigenic test with more details specified in [Table 3](#) below.

Table 3: Rules to Derive Similarity and Antigenic Match using Culture Antigenic and Genetic Sequencing Test Results

| | | Sequencing test result | | |
|----------------------------------|-------------|--------------------------|--------------------------|--------------------------|
| | | Similar | Not Similar | Unknown/Not Reportable |
| Culture antigenic testing result | Matched | Matched and Similar | Matched and Similar | Matched and Similar |
| | Not Matched | Not Matched; Not Similar | Not Matched; Not Similar | Not Matched; Not Similar |

| | Unknown/Not Reportable | Similar but Unknown Antigenically | Not Similar and Unknown Antigenically | Unknown for Both |
|--|-------------------------------|-----------------------------------|---------------------------------------|------------------|
|--|-------------------------------|-----------------------------------|---------------------------------------|------------------|

When deriving similarity, the culture result (if available) will take precedence over the sequencing result. The sequencing test provides additional information when the culture result is unavailable.

After the identification of a RT-PCR confirmed protocol-defined ILI, the results from the subsequent viral culture antigenic test and/or the genomic sequencing test on the NP-swab sample may be unavailable to confirm antigenic match or similarity to the selected vaccine strains. The main reasons include 1) damaged/lost sample; 2) unsuccessful amplification and/or culturing in laboratory processing; and 3) tests not done due to a local certified laboratory being used.

In the third case (a local certified laboratory test is used for RT-PCR confirmation), an NP-swab sample may be collected and processed by the central laboratory at a later time. If another positive RT-PCR test exists within 7 days of the confirming positive RT-PCR date and subsequent antigenic test and/or genomic sequencing test results are available, then the information from this test can be used to derive the similarity and antigenic match, following the same logic described above.

If a positive RT-PCR test does not exist to provide supplemental information, then the antigenic match and/or similarity results will be considered missing.

The time to the first identified episode for the key secondary efficacy endpoints, in days, will be calculated as: Start date of the first identified episode – Date of randomization + 1.

Cases will be counted for each of the two key secondary efficacy endpoints when the first identified episode starts 14 days after the vaccination and up to Day 181/ Month 6 or at the end of the influenza season whichever ends later. i.e.

$$\begin{aligned} & \text{Vaccination date} + 14 \leq \text{Start date of the first identified episode} \\ & \leq \text{Date of Day 181/ Month 6 or at the end of the influenza season, whichever occurs later.} \end{aligned}$$

6.3.2.2. Analysis of the Key Secondary Efficacy Endpoints

The same primary, sensitivity, and supportive analysis methods as described for the primary efficacy endpoint ([Section 6.3.1.2](#)) will be applied to the key secondary efficacy endpoints based on the PP and mITT Sets, unless otherwise specified.

As for the primary efficacy endpoint, potential intercurrent events for key secondary efficacy endpoints may include:

1. Early discontinuation or death unrelated to influenza; or
2. Early ILI up to 14 days after study vaccination.

The same intercurrent event handling approach used for the primary efficacy endpoints will be used to address the intercurrent events for the analysis of key secondary efficacy endpoints.

Similar censoring rules as for the primary efficacy endpoint will be applied. Participants without RT-PCR confirmed protocol-defined ILI with similarity to selected influenza A or B virus strains for the seasonal influenza vaccine will be censored at Day 181 (Month 6) or at the end of the influenza season (whichever occurs later), or at the date of early discontinuation or death unrelated to influenza, whichever is earliest. Participants with early RT-PCR confirmed protocol-defined ILI up to 14 days after the study vaccination will be censored at the start date of the earliest RT-PCR confirmed protocol-defined ILI.

Participants without RT-PCR confirmed protocol-defined ILI with antigenically matched to selected influenza A or B virus strains for the seasonal influenza vaccine will be censored at Day 181 (Month 6) or at the end of the influenza season (whichever occurs later), or at the date of early discontinuation or death unrelated to influenza, whichever is earliest. Participants with early RT-PCR confirmed protocol-defined ILI up to 14 days after the study vaccination (start date of the RT-PCR confirmed ILI \leq vaccination date +13) will be censored at the start date of the earliest RT-PCR confirmed protocol-defined ILI.

In addition, after the first RT-PCR confirmed ILI is confirmed, the antigenic match and/or similarity (see [Section 6.3.2.1](#)) is negative or the result is missing, the observation will be censored at the ILI start date for the corresponding key secondary efficacy endpoints.

The following analyses will be conducted at the final analysis for each of the key secondary efficacy endpoints.

6.3.2.2.1. Analysis for Noninferiority

Relative vaccine efficacy will be estimated using a stratified Cox proportional hazard model including study vaccination group as a fixed effect to estimate the HR (mRNA-1010 vs. active comparator) at a one-sided 2.5% significance level based on the PP Set. The stratification factors at randomization ([Section 4.4](#)) will be applied as the strata variables. Efron's method will be used to handle ties. The rVE will be estimated along with the two-sided 95% CI and one-sided p-value for testing $H_0^1: rVE \leq -10\%$ (inferior).

Noninferiority will be demonstrated if the one-sided p-value for rejecting $H_0^1: HR \geq 1.1$ (equivalently, $H_0^1: rVE \leq -10\%$) is less than 2.5%, on the PP Set at the final analysis.

As a sensitivity analysis, the analysis of the key secondary efficacy endpoints for NI will be repeated on the mITT Set. In addition, another sensitivity analysis for the NI of the key secondary efficacy endpoints will be performed using the actual stratification factors (CRF derived) on the PPS Set.

6.3.2.2.2. Analysis for Superiority

If the NI of mRNA-1010 vs. active comparator is demonstrated using the PP Set, superiority of mRNA-1010 vs. active comparator will be evaluated using the same key efficacy endpoint on the mITT Set, at the final analysis.

Superiority will be demonstrated if the one-sided p-value for rejecting $H_0^2: HR \geq 1$ (equivalently, $H_0^2: rVE \leq 0\%$) is less than 2.5%, on the mITT Set.

As a sensitivity analysis, the analysis of the key secondary efficacy endpoints for superiority will be repeated on the PP Set. In addition, another sensitivity analysis for the superiority of the key secondary efficacy endpoints will be performed using the actual stratification factors (CRF derived) on the mITT Set.

6.3.2.2.3. Supportive Analyses

The same method used for the primary endpoint based on the incidence rate and stratified log rank test will be performed on the mITT set as a supportive analysis if the NI for the corresponding key secondary endpoint(s) is demonstrated.

6.3.2.2.4. Subgroup Analysis

Similar subgroup analysis for NI as used for the primary endpoint may be performed on the PP Set if sufficient case numbers of the key secondary endpoints have been observed. Subgroup analysis may be performed for the superiority test on mITT Set if the NI for the corresponding key secondary endpoint is demonstrated.

6.3.3. Analysis of the Other Secondary Efficacy Endpoints

6.3.1.1. Derivation of Cases for Other Secondary Efficacy Endpoints

6.3.1.2. RT-PCR Confirmed US CDC-defined ILI

The secondary efficacy endpoints for RT-PCR confirmed US CDC-defined ILI starting 14 days post vaccination through Day 181 (Month 6) or at the end of influenza season are as follows:

- rVE of mRNA-1010 vs. the active comparator to prevent the occurrence of the first episode of RT-PCR confirmed US CDC-defined ILI starting 14 days post vaccination through Day 181 (Month 6) or at the end of the influenza season, whichever occurs later, caused by any influenza A or B strains regardless of antigenic match.
- rVE of mRNA-1010 vs. the active comparator to prevent the occurrence of the first episode of RT-PCR confirmed US CDC-defined ILI starting 14 days post vaccination through Day 181 (Month 6) or at the end of the influenza season, whichever occurs later, caused by influenza A or B virus strains with similarity to vaccine strains.
- rVE of mRNA-1010 vs. the active comparator to prevent the occurrence of the first episode of RT-PCR confirmed US CDC-defined ILI starting 14 days post

vaccination through Day 181 (Month 6) or at the end of the influenza season, whichever occurs later, caused by influenza A or B virus strains that are antigenically matched to vaccine strains.

The first RT-PCR confirmed US CDC-defined ILI is derived as the first RT-PCR confirmed protocol-defined ILI case (see derivation rules in [Section 6.3.1.1](#)) which also meets the US CDC-defined ILI definition: The presence of temperature ≥ 37.8 °C [≥ 100 °F], accompanied by at least one of the respiratory illness symptoms (cough and/or sore throat).

The confirmations of similarity and antigenic match follow those for the key secondary efficacy endpoints as described in [Section 6.3.2.1](#) and [Table 3](#).

The time to first identified episode for the secondary efficacy endpoints, in days, will be calculated as: Start date of the first identified episode – Date of randomization +1.

Cases will be counted for the secondary efficacy endpoints when the first identified episode for the other secondary endpoints starts 14 days after the vaccination and up to Day 181 (Month 6) or at the end of the influenza season whichever occurs later, i.e.,

Vaccination date + 14 \leq Start date of the first episode for the secondary efficacy endpoint \leq Date of Day 181/ Month 6 or at the end of the influenza season, whichever occurs later.

6.3.1.3. Culture-Confirmed Protocol-Defined ILI

The secondary efficacy endpoint for culture-confirmed protocol-defined ILI starting 14 days post vaccination through Day 181 or at the end of the influenza season are as follows:

- rVE of mRNA-1010 vs. the active comparator to prevent the occurrence of the first episode of culture-confirmed protocol-defined ILI starting 14 days post vaccination through Day 181 (Month 6) or at the end of the influenza season, whichever occurs later, caused by any influenza A or B strains.

The derivation rules for the first culture-confirmed protocol-defined ILI caused by any influenza A or B virus strains (see definition in [Section 3.2.2](#)) are as follows:

- Must be the first RT-PCR confirmed protocol-defined ILI ([Section 6.3.1.1](#))

- Must be confirmed by a positive result for influenza infection by viral culture using the stored NP-swab sample

As for the key secondary efficacy endpoints, when a local certified laboratory is used for the RT-PCR test, the viral culture test cannot be performed on the NP swab sample. If another qualified positive RT-PCR test with subsequent viral culture test result (positive or negative) is available, then the same search criteria (positive RT-PCR dates within 7 days) will be implemented.

The time-to-first identified culture-confirmed protocol-defined ILI, in days, will be calculated as: Start date of the first identified episode – Date of randomization + 1.

Cases will be counted when the first identified episode of culture-confirmed protocol-defined ILI starts 14 days after the vaccination and up to Day 181 (Month 6) or at the end of the influenza season whichever occurs later, i.e.,

$$\text{Vaccination date} + 14 \leq \text{Start date of the first culture-confirmed protocol-defined ILI} \leq \text{Date of Day 181 / Month 6 or at the end of the influenza season, whichever occurs later.}$$

6.3.1.4. Culture-Confirmed US CDC-Defined ILI

The secondary efficacy endpoint for culture-confirmed US CDC-defined ILI starting 14 days post vaccination through Day 181 or at the end of the influenza season are as follows:

- rVE of mRNA-1010 vs. the active comparator to prevent the occurrence of the first episode of culture-confirmed US CDC-defined ILI starting 14 days post vaccination through Day 181 (Month 6) or at the end of the influenza season, whichever occurs later, caused by any influenza A or B strains.

A culture-confirmed US CDC-defined ILI case is defined as a positive result for influenza infection by viral culture following a positive result for influenza infection by RT-PCR, together with eligible symptoms ([Section 3.2.2](#)).

The derivation rules for the first culture-confirmed US CDC-defined ILI caused by any influenza A or B virus strains are as follows:

- Must be the first RT-PCR confirmed US CDC-defined ILI ([Section 6.3.2.3.1](#))

- Must be confirmed by a positive result for influenza infection by viral culture using the stored NP-swab sample

As for the key secondary efficacy endpoints, when a local certified laboratory is used for the RT-PCR test without a viral culture on the NP swab sample, another qualified positive RT-PCR test with subsequent viral culture antigenic match result (positive or negative) can be used. The same search criteria (positive RT-PCR dates within 7 days) will be implemented.

The time to first identified culture-confirmed US CDC-defined ILI, in days, will be calculated as: Start date of the first culture-confirmed US CDC-defined ILI – Date of randomization + 1.

Cases will be counted when the first identified episode of culture-confirmed US CDC-defined ILI starts 14 days after the vaccination and up to Day 181 (Month 6) or end of influenza season whichever occurs later, i.e.,

Vaccination date + 14 \leq Start date of the first culture-confirmed US CDC-defined ILI \leq Date of Day 181/ Month 6 or at the end of the influenza season, whichever occurs later.

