
 To evaluate relative vaccine efficacy of mRNA-1010 vaccine as compared to an active comparator against influenza caused by influenza A or B strains antigenically matched to the vaccine strains^b using protocol-defined ILI definition. 	
 First episode of RT-PCR confirmed protocol-defined ILI that begins at least 14 days after vaccination through Day 181 (Month 6)/end of influenza season caused by influenza A or B strains antigenically matched to the vaccine strains^b selected for the seasonal vaccine.

 To evaluate relative vaccine efficacy of mRNA-1010 vaccine as compared to an active comparator against influenza caused by influenza A or B strains (any strains or similar strains or antigenically matched strains) using CDC-defined ILI definition. 	
 First episode of RT-PCR confirmed US CDC-defined ILI that begins at least 14 days after vaccination through Day 181 (Month 6)/end of influenza season caused by 
 Any influenza A or B strains; Influenza A or B strains with similarity to vaccine strains;

Primary Objectives	Primary Endpoints
	
 – Influenza A or B strains that are antigenically matched to vaccine strains.

 • To evaluate relative vaccine efficacy of mRNA-1010 vaccine as compared to an active comparator against culture-confirmed influenza caused by any influenza A or B strains. 	
 • First episode of culture-confirmed protocol-defined ILI that begins at least 14 days post vaccination through Day 181 (Month 6)/end of influenza season caused by any influenza A or B strains regardless of antigenic match to strains selected for the seasonal vaccine. • First episode of culture-confirmed CDC-defined ILI that begins at least 14 days post vaccination through Day 181 (Month 6)/end of influenza season caused by any influenza A or B strains regardless of antigenic match to strains selected for the seasonal vaccine.

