8.10.5. Influenza-like Illness Case Definitions

Protocol-defined ILI:

A protocol-defined ILI is defined as body temperature $\geq 37.5^{\circ}\text{C}$ [$\geq 99.5^{\circ}\text{F}$] accompanied by at least 1 respiratory illness symptom (sore throat, cough, sputum production, wheezing, or difficulty breathing).

CDC-defined ILI:

A CDC-defined ILI is defined as body temperature $\geq 37.8^{\circ}\text{C}$ ($\geq 100^{\circ}\text{F}$) accompanied by cough and/or sore throat.

RT-PCR-confirmed Influenza Infection:

An RT-PCR-confirmed influenza infection is defined as a positive influenza result on a respiratory sample by RT-PCR within 7 days of onset of protocol- or CDC-defined ILI performed at any setting during the study period.

Culture-confirmed Influenza Infection:

Culture-defined ILI is defined as a positive influenza result by viral culture following a positive influenza result by RT-PCR. Viral cultures will only be done on samples with a positive influenza result by RT-PCR.

Similarity to Strains Selected for the Seasonal Vaccine:

A laboratory-confirmed isolate is deemed similar to one of the vaccine components if determined by antigenic testing of the cultured virus using specific antisera and/or by genetic sequencing of the HA segments showing identity of key antigenic residues with vaccine strain-like strains.

Antigenic Matched to Strains Selected for the Seasonal Vaccine

Culture-confirmed viruses are deemed to be antigenically similar to vaccine strains by antigenic testing of the cultured virus using specific antisera.

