Culture-confirmed protocol-defined ILI is defined based on the following criteria:

1. The participant must have experienced the following symptoms: Body temperature $\geq 37.5^{\circ}\text{C}$ [$\geq 99.5^{\circ}\text{F}$] **accompanied by** at least **ONE** of respiratory illness symptom: sore throat, cough, sputum production, wheezing, or difficulty breathing.

AND

2. The participant must have a positive result for influenza infection by viral culture following a positive result for influenza infection by RT-PCR performed within 7 days after protocol-defined ILI symptom onset. Viral cultures will only be done on samples with a positive result for influenza infection by RT-PCR.

Culture-confirmed US CDC-defined ILI is defined based on the following criteria:

1. The participant must have experienced the following symptoms: Body temperature $\geq 37.8^{\circ}\text{C}$ [$\geq 100^{\circ}\text{F}$] **accompanied by** at least **ONE** respiratory illness symptom: cough, and/or sore throat.

AND

2. The participant must have a positive result for influenza infection by viral culture following a positive result for influenza infection by RT-PCR performed within 7 days after US CDC-defined ILI symptom onset. Viral cultures will only be done on samples with a positive result for influenza infection by RT-PCR.

RT-PCR confirmed ILI caused by specific influenza A strain

- rVE of mRNA-1010 vaccine vs. the active comparator to prevent the occurrence of the first episode of RT-PCR confirmed protocol-defined ILI that begins at least 14 days after vaccination through Day 181 (Month 6) or end of influenza season, whichever occurs later, caused by influenza A strain that is antigenically matched to the vaccine strain H1N1.
- rVE of mRNA-1010 vaccine vs. the active comparator to prevent the occurrence of the first episode of RT-PCR confirmed protocol-defined ILI that begins at least 14 days after vaccination through Day 181 (Month 6) or end of influenza season, whichever occurs later, caused by influenza A strain that is antigenically matched to the vaccine strain H3N2.
- rVE of mRNA-1010 vaccine vs. the active comparator to prevent the occurrence of the first episode of RT-PCR confirmed protocol-defined ILI that begins at least 14 days after vaccination through Day 181 (Month 6) or end of influenza season, whichever occurs later, caused by influenza A strain that is antigenically matched to the vaccine strain H1N1 and/or H3N2.

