As for the key secondary efficacy endpoints, when a local certified laboratory is used for the RT-PCR test without a viral culture on the NP swab sample, then another qualified positive RT-PCR test with subsequent viral culture antigenic match result (positive or negative) can be used. The same search criteria (positive RT-PCR dates within 7 days) will be implemented.

The time to the first identified episode for each of these secondary efficacy endpoints, in days, will be calculated as: Start date of the first identified episode – Date of randomization + 1.

A participant will be counted as a culture-confirmed US CDC-defined ILI case caused by a specific influenza strain if the first identified episode for each of these secondary efficacy endpoints starts 14 days after the vaccination and up to Day 181 (Month 6) or at the end of the influenza season whichever occurs later, i.e.,

$$\text{Vaccination date} + 14 \leq \text{Start date of the first identified episode} \\ \leq \text{Date of Day 181/ Month 6 or at the end of the influenza season, whichever occurs later.}$$

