6.3.1.7. Analysis of Other Secondary Efficacy Endpoints

For each of the other secondary efficacy endpoints discussed in [Section 6.3.2.3.1 – 6.3.2.3.4](#), a stratified Cox proportional hazards model will be used to estimate the HR. Relative vaccine efficacy will be estimated along with two-sided 95% CI based on the PP and mITT Sets.

Intercurrent events, missing data, and censoring rules will be similar to those for the primary and key secondary efficacy endpoints, where applicable. After the first RT-PCR confirmed protocol-defined ILI is identified, if any additional condition required for the other efficacy endpoint is not met or cannot be determined, the observation will be censored at the ILI start date for the corresponding other secondary efficacy endpoints.

The other secondary efficacy endpoint discussed in [Section 6.3.2.3.5](#) will be analyzed as follows:

- rVE of mRNA-1010 vs. the active comparator in preventing hospitalizations associated with RT-PCR confirmed protocol-defined ILI starting 14 days post vaccination through Day 181 (Month 6) or the end of the influenza season, whichever occurs later, caused by any strain of influenza virus regardless of antigenic match to the strains selected for the seasonal vaccine

The number and percentage of participants with at least one case will be summarized by vaccination group.

The rVE will be estimated by one minus the ratio of observed incidence rates (mRNA-1010 vs. active comparator) multiplied by 100%:

$$\text{rVE} = 100 \times (1 - [(C_{\text{mRNA}}/N_{\text{mRNA}}) / (C_{\text{control}}/N_{\text{control}})]) \%,$$

where C_{mRNA} and $C_{control}$ are the number of cases per the hospitalizations associated with RT-PCR confirmed protocol-defined ILI efficacy endpoint definition in the mRNA-1010 group and the active comparator group respectively, and N_{mRNA} and $N_{control}$ are the number of participants in the mRNA-1010 group and the active comparator group, respectively.

A 2-sided 95% CI for rVE will be calculated based on Farrington and Manning's score method ([Farrington and Manning 1990](#)) based on the PP and mITT Sets.

The above analyses of secondary efficacy endpoints are not controlled for multiplicity.

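### SAP 6.3.1.4 names the antigenic-match result instead of the culture result in its substitute-swab rule for culture-confirmed CDC-defined ILI

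*SAP*

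**What the plan says.** **What makes a case.** Table 2 in Protocol Section 3 describes the endpoint as a first culture-confirmed CDC-defined ILI "caused by any influenza A or B strains regardless of antigenic match to strains selected for the seasonal vaccine". Protocol 8.10.5 defines the laboratory part: "Culture-defined ILI is defined as a positive influenza result by viral culture following a positive influenza result by RT-PCR". SAP 3.2.2 repeats it: "The participant must have a positive result for influenza infection by viral culture following a positive result for influenza infection by RT-PCR". The derivation list in SAP 6.3.1.4 agrees: "Must be confirmed by a positive result for influenza infection by viral culture using the stored NP-swab sample". None of these places mentions antigenic match as a condition.

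**What happens when a local laboratory did the RT-PCR.** The swab that confirmed the case was then not cultured centrally. The SAP lets the analyst use a second positive RT-PCR swab dated within 7 days, a search rule set out in 6.3.2.1 and carried into the later sections. Three sections state which result from that second swab is used:

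- 6.3.1.3, culture-confirmed protocol-defined ILI: "If another qualified positive RT-PCR test with subsequent viral culture test result (positive or negative) is available".
- 6.3.1.4, culture-confirmed CDC-defined ILI: "another qualified positive RT-PCR test with subsequent viral culture antigenic match result (positive or negative) can be used".
- 6.3.1.5, ILI caused by strains matched to the vaccine H1N1 or H3N2 component: "then another qualified positive RT-PCR test with subsequent viral culture antigenic match result (positive or negative) can be used".

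**What happens if confirmation fails.** SAP 6.3.1.7 says that "if any additional condition required for the other efficacy endpoint is not met or cannot be determined, the observation will be censored", with the ILI start date as the censoring date. Table 14 in Appendix I has a corresponding row for the culture-confirmed endpoints.

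**The concern.** Growing virus from a swab and typing the isolate against vaccine-specific antisera are two tests, and the second can be done only after the first has succeeded. Table 3 in SAP 6.3.2.1 allows for an antigenic result that is unknown or not reportable. A rule that asks for the typing result therefore asks for more than the endpoint needs.

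The wording in 6.3.1.4 fits 6.3.1.5, where match is part of the endpoint. It does not fit an endpoint that counts any strain. The two culture-confirmed endpoints differ in their symptom criteria, and nothing in the documents gives a reason for them to differ in the laboratory criterion as well.

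At stake is the case status of some locally confirmed participants on a secondary endpoint listed in the protocol, and the consistency of that endpoint with its sister. A programmer who codes the sentence as written may also reach a different case list from one who codes the endpoint definition.

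**Working it through.** No arithmetic applies: the plan gives no figure for this rule, and the point depends on no sample size, alpha or event count. The check is to follow one participant through the text.

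Take a participant whose first RT-PCR-confirmed illness meets the CDC definition, was confirmed by a local laboratory, and has a second, centrally processed positive swab within the 7-day window. The second swab can have four outcomes.

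| Second swab | 6.3.1.3 (protocol-defined) | 6.3.1.4 (CDC-defined), read literally |
|---|---|---|
| (a) Culture positive, matched | Case | Case |
| (b) Culture positive, not matched | Case | Accepted as a substitute, because a negative match result is allowed; a case under the positive-culture criterion |
| (c) Culture positive, antigenic result not reportable | Case | The named result does not exist; confirmation can be treated as undetermined and the participant censored |
| (d) Culture negative | Not a case | Not a case |

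Outcomes (a) and (d) give the same answer under both rules. Outcome (b) also agrees if the sentence is read together with the positive-culture criterion in the same section. Outcome (c) is where the rules part. The swab has the culture result that 6.3.1.3 asks for but not the antigenic-match result that 6.3.1.4 asks for, and 6.3.1.7 censors where a required condition cannot be determined.

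The number of participants affected is a product of four terms:

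locally confirmed cases × share with a second central positive swab within 7 days × share of those swabs that are culture positive with no reportable antigenic result × share of those illnesses that meet the CDC definition.

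The documents give none of the four, so the product cannot be evaluated. It is zero if outcome (c) never occurs.

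**The case against.** The strongest reply is that the disputed sentence does not define a case. It only points to another swab that may stand in, and it says so permissively: a swab with a match result can be used, with no statement that a swab without one cannot. The case criterion in the same section remains a positive culture. On that view the required condition in 6.3.1.7 is also a positive culture, and the Table 14 row, which censors only when no event meets the endpoint's definition, would not remove a culture-positive participant.

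Much of this stands, and it disposes of two stronger readings that a reader might infer.

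- **Not-matched isolates drop out, so the endpoint depends on match.** The text does not support this. The sentence accepts match results of either sign, and an isolate that could be typed has grown in culture and so meets the criterion.
- **Untyped swabs are barred outright.** The text does not say this either. It fails to name their result as usable, which leaves a gap but does not state an exclusion.

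It is also fair to say that the unknown or not-reportable row of Table 3 should not be equated with culture-positive, untyped swabs. The reasons that 6.3.2.1 lists for missing results include lost samples and failed culture, and such swabs are not cases under either rule. The documents do not show that outcome (c) occurs.

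What the reply does not remove is the ambiguity for outcome (c). The favourable reading has to be supplied by the reader, whereas 6.3.1.3 states it. The protocol definition does not settle the matter automatically, because the SAP introduction says that the SAP prevails where methods differ, and SAP Section 7 declares no changes from the protocol.

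**Conclusion.** The point holds as a minor inconsistency in a stated derivation rule. SAP 6.3.1.4 names a result that its own endpoint does not need, and 6.3.1.3 names the right one for the same situation. The near-identical sentence in 6.3.1.5 suggests carried-over wording. So does the fact that 6.3.1.5, which covers RT-PCR-confirmed protocol-defined illness, describes its own participants as culture-confirmed CDC-defined cases. That explanation is an inference, and the conclusion does not rest on it.

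The possible loss is confined to locally confirmed participants whose substitute swab is culture positive without a reportable antigenic result, and it arises only if the sentence is applied literally. The size is unknown and may be zero; any case count would rest wholly on assumed shares. The endpoint is an other secondary endpoint, outside the hierarchy, without multiplicity control and with no formal test planned. The primary and key secondary analyses, their case targets, alpha and power are unaffected.

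**What to change.** In the substitute-swab sentence of SAP 6.3.1.4, replace the reference to the antigenic-match result with the viral culture test result, positive or negative, in the terms used in 6.3.1.3. Leave the match wording in 6.3.1.5, where match defines the endpoint. Check that the code for the two culture-confirmed endpoints uses the same laboratory criterion, so that they differ only in the symptom definition.

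The cost is one phrase in the SAP and the matching lines of derivation code. No new data are needed.
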